10.2.1. Primary Analysis

10.2.2. Safety Analyses

Subject evaluation groups will show end of study subject disposition and will show which subjects were analysed for pharmacokinetics (PK), and for safety (adverse events and laboratory data). Subject counts will be supplied for subject discontinuation(s) by treatment.

A summarization of demographic data will be provided for age, race, weight, and height. Each will be summarized by sex at birth in accordance with the sponsor reporting standards.

- Discontinuations, adverse events, laboratory data, vital signs, ECG and concomitant medication data will be summarized by treatment and in accordance with current Pfizer data standards. The adverse event risk difference will be summarized by treatment group. No p values and no multiplicity adjustments will be provided.

10.2.2.1. Laboratory Data

Laboratory data outlined in the study protocol will be summarized by study days, and listed in accordance with the sponsor reporting standards. For each planned timepoint, observed values and change from baseline values within each treatment will be summarized with

descriptive statistics. For laboratory parameters with categorical outcomes, subjects counts will be presented for each visit. No screening laboratory values will be presented in the summary tables. Line plots on mean ($\pm 2*SE$) will be generated.

10.2.2.2. Vital Signs Data

Observed values and changes from baseline in supine systolic and diastolic blood pressures, and pulse rate will be summarized by treatment and day. For each planned timepoint, observed values and change from baseline values within each treatment will be summarized with descriptive statistics (using sponsor default standards). Mean observed values, and mean changes from baseline will be plotted separately. On each plot there will be separate lines for each treatment, dose group against study day. Data from all treatments will be plotted on the same figure. Plots with and without ($\pm SE$) will be produced. For changes from baseline, the differences between each time point and baseline will be summarized (N, mean, 90% confidence interval) and plotted (mean) for each dose and time point (including baseline).

Maximum values and changes from baseline will be summarized descriptively by treatment using categories as defined in Appendix 1. Numbers and percentages of subjects meeting the categorical criteria will be provided. All planned and unplanned postdose timepoints will be counted in these categorical summaries. All values meeting the criteria of potential clinical concern will be listed.

These data will be listed in accordance with the sponsor reporting standards.

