4.2. Exclusion Criteria

Subjects presenting with any of the following will not be included in the study:

Exclusions for General Health

1. History of type 1 diabetes mellitus
2. Evidence or history of diabetic complications with significant end-organ damage including but not limited to:
 - proliferative retinopathy;
 - macular edema;
 - diabetic nephropathy;
 - severe neuropathy;
 - neuropathic ulcers.
3. History of chronic pancreatitis or at high risk for pancreatitis including but not limited to gall bladder disease, hypertriglyceridemia, hypercalcemia, or alcohol abuse.
4. Risk of pancreatic neuroendocrine neoplasm including but not limited to personal or family history of islet cell tumor, multiple endocrine neoplasia 1 (MEN) syndrome, Von Hippel-Lindau syndrome or neurofibromatosis.
5. History of severe hypoglycemia (ie, requiring assistance) or hypoglycemia unawareness within 1 year of randomization.
6. Poorly controlled hypertension (systolic blood pressure >160 mm Hg or a diastolic blood pressure >90 mm Hg, even with treatment). Subjects who have hypertension and are controlled on stable dosages of anti-hypertensive medications can be included.
7. History of a cardiovascular or cerebrovascular event or procedure (eg, MI, stroke, stent) within one year of randomization.
8. Heart failure, NY Class 2, 3, 4.
9. Past or current history of alcoholism or drug addiction according to Diagnostic Statistical Manual (DSM) IV criteria, or use of any recreational drugs within 12 months prior to the first Screening visit.
10. History of diabetic ketoacidosis (DKA), hyperosmolar coma, or lactic acidosis.

11. History of cancer within the last 5 years (except for cutaneous basal cell or squamous cell cancer resolved by excision).
12. Regular alcohol consumption >2 drinks/day (1 drink = 5 ounces [150 mL] of wine or 12 ounces [360 mL] of beer or 1.5 ounces [45 mL] of hard liquor) within 30 days prior to the first Screening visit.
13. Blood donation (excluding plasma donations) of approximately 1 pint (500 mL) or more within 56 days prior to dosing or plans to donate during the conduct of the study.
14. Evidence or history of clinically significant hematological, renal, endocrine, pulmonary, gastrointestinal, cardiovascular, immunologic, hepatic, psychiatric, neurologic, or allergic disease (exception: untreated, asymptomatic, seasonal allergies at the time of dosing allowed) unless deemed not clinically significant by the Investigator and Sponsor.

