10.2.2.5. Ambulatory Blood Pressure Monitoring (ABPM)

For MAD portion of the study, ambulatroy blood pressure (ABP) reading will be acquired using the ABPM equipment provided by Biomedical Systems to evaluate potential treatment effect on ABP. Ambumlatory blood pressure are scheduled to be recorded at the following visits:

Table 7. ABPM Visit Schedule

Protocol Visit	Visit code to be selected
Day-2 / Day -1	Day -2
Day 1/ Day 2	Day 1
Day 7/ Day 8	Day 7
Day 63/ Day 64	Day 63
Day 84/ Day 85	Day 84
Unscheduled	UNS
Certification	CERT
Test	TEST

Summary of ABPM measures mSBP, mDBP, mHR, and mMAP represent weighted means of systolic blood pressure, diastolic blood pressure, heart rate and mean arterial pressure (MAP), respectively, and will be summarized in three time increments for a given measurement period: 24 Hour, Day Time (06:00 – 22:00), and Night Time (22:00 – 06:00). mXXX will be calculated using an area under the curve approach over the collection time interval, normalized by the time interval: $AUC(0-t) / t$. Mean over study days by treatment line plots will be produced along with spaghetti plots of individual profiles over study days grouped by treatment. The number and percentage of subjects with SBP > 140 mmHg, and DBP > 90 mmHg will be tabulated by treatment and Study Day, respectively. Additionally, mSBP, mDBP, mHR, and mMAP response will be modelled using a MMRM with corresponding baseline as covariate, and treatment and visit as fixed factors. Mean change from baseline over time with active treatment may be compared to the mean change from baseline over time with pooled placebo treated subjects using MMRM analysis with treatment, visit, and visit by treatment as fixed effects, subject as a random effect, and baseline value as covariate adopting unstructured covariance structure. For displaying purpose, Mean(\pm SE) of hourly average of absolute SBP, DBP, HR, MAP, and change from baseline will be plotted by Study Day and 24-hour time per treatment group; by treatment and 24-hour time per Study Day. Line plots of individual 20-min measurements of each subject will be plotted by study Day and time, and group by treatment and dose group. Least square means (\pm SE) of day Time, Night Time, and 24 Hour mSBP, mDBP, mHR, and mMAP will be plotted by treatment and Study Day. If warranted, a longitudinal Emax model may be developed to further characterize the potential treatment effect on ABPM.

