Appendix 2. Categorical Classes for Vital Signs, QTcF, PR and QRS

Categories for Vital Signs

Systolic BP (mm Hg)	min. <90	
Systolic BP (mm Hg) change from baseline	max. decrease ≥30	max. increase ≥30
Diastolic BP (mm Hg)	min. <50	
Diastolic BP (mm Hg) change from baseline	max. decrease ≥20	max. increase ≥20
Supine pulse rate (bpm)	min. <40	max. >120
Standing pulse rate (bpm)	min. <40	max. >140

- Measurements that fulfill these criteria are to be listed in Appendix A of the report

Categories for QTcF

QTcF (ms)	450≤ max. <480	480≤ max.<500	max. ≥500
QTcF (ms) increase from baseline	30≤ max. <60	max. ≥60	

Categories for PR and QRS

PR (ms)	max. ≥300	
PR (ms) increase from baseline	Baseline >200 and max. ≥25% increase	Baseline ≤200 and max. ≥50% increase
QRS (ms)	max. ≥200	
QRS (ms) increase from baseline	Baseline >100 and max. ≥25% increase	Baseline ≤100 and max. ≥50% increase

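### The SAP promises category counts of maximum blood pressure, but its category table has no absolute upper category for systolic or diastolic pressure

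*SAP*

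**What the plan says.** SAP 10.2.2.2 deals with supine systolic pressure, diastolic pressure and pulse rate. Besides descriptive statistics by timepoint it commits to a categorical summary: "Maximum values and changes from baseline will be summarized descriptively by treatment using categories as defined in Appendix 1". Two further commitments follow: "Numbers and percentages of subjects meeting the categorical criteria will be provided", and "All values meeting the criteria of potential clinical concern will be listed". Both planned and unplanned post-dose readings enter this categorical summary.

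Appendix 1 is the visit-window table. The vital-sign categories are in Appendix 2. For systolic pressure these are a minimum below 90 mm Hg and, in the row "Systolic BP (mm Hg) change from baseline", a decrease of at least 30 or "max. increase ≥30". Diastolic pressure has a minimum below 50 and changes of at least 20 either way. Pulse rate has both a lower and an upper absolute limit. The table also has a row for "Standing pulse rate (bpm"), although the protocol schedules only supine pulse.

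The SAP does set upper blood pressure limits elsewhere. Section 10.2.2.5 tabulates "subjects with SBP > 140 mmHg, and DBP > 90 mmHg", but for ambulatory monitoring, which only the MAD cohorts have.

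On entry values, protocol 4.2, criterion 6, excludes "Poorly controlled hypertension (systolic blood pressure >160 mm Hg or a diastolic blood pressure >90 mm Hg, even with treatment"), so a reading of 160/90 is eligible.

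**The concern.** The text promises categories for maximum values, and the table supplies none for blood pressure. Pulse rate does get an upper limit in the same table. The only route by which a high cuff pressure can be counted is the size of its rise, so a subject who starts high can reach a clearly raised value without meeting any criterion.

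Safety and tolerability are the primary objective, and the MAD part adds dedicated ambulatory monitoring of blood pressure. Most dose groups have 6 to 8 active subjects, so individual outliers carry much of the information and group means dilute them. The categorical summary is the output designed to bring such subjects forward, and it counts unplanned readings too. At stake is whether a reader of that table and its companion listing would see high cuff pressures as readily as low ones.

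**Working it through.** There is no sample size, power or event figure to reproduce. The check applies the Appendix 2 criteria as a rule.

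**Step 1. Set the promise beside the table.**

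| Parameter | Absolute lower category | Absolute upper category | Upward change category |
|---|---|---|---|
| Systolic (mm Hg) | <90 | none | ≥30 |
| Diastolic (mm Hg) | <50 | none | ≥20 |
| Supine pulse (bpm) | <40 | >120 | none |

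The maximum-value summary can be built for pulse rate but not for either pressure.

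**Step 2. Find the highest reading that meets no criterion.** Inputs:
- change limits of 30 and 20 mm Hg (SAP Appendix 2)
- readings recorded to the nearest mm Hg (protocol 7.2.4)
- highest eligible pressure 160/90 (protocol 4.2, criterion 6)

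In whole mm Hg, the largest rise that does not count is 30 − 1 = 29 systolic and 20 − 1 = 19 diastolic. The highest uncounted reading is therefore (baseline systolic + 29)/(baseline diastolic + 19):

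| Baseline | Highest reading meeting no criterion |
|---|---|
| 130/80 | 159/99 |
| 140/85 | 169/104 |
| 150/90 | 179/109 |
| 160/90 | 189/109 |

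In each row, one more mm Hg in either component would meet a criterion.

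**Step 3. Check how firm 189/109 is.** SAP section 8, Table 3, defines baseline pressure as the mean over Days -1 and 1 (SAD) or Days -2, -1 and 1 (MAD), not the screening value. It can fall on either side of the entry limit and need not be a whole number. The last row is an illustration, not a bound.

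**Step 4. Check whether the ambulatory counts fill the gap.**
- SAD has no ambulatory monitoring. All planned SAD subjects (5 cohorts × 8 = 40) have cuff readings only.
- MAD has five scheduled recordings, starting on Days -2, 1, 7, 63 and 84. The first is baseline, which leaves 5 − 1 = 4 on treatment.
- No ambulatory recording is scheduled on dosing Days 29 and 57, when cuff pressure is taken before dosing and at 1, 2 and 4 hours, or on follow-up Days 99, 113, 141 and 169.

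The counts above 140 and 90 therefore do not reach SAD, or the MAD cuff readings outside the ambulatory days.

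**Step 5. Check where an uncounted reading still shows.** SAP 10.1 puts all data in listings and includes the maximum among its descriptive statistics. SAP 10.2.2.2 applies descriptive statistics at each planned timepoint and lists the vital-sign data. A planned reading thus appears in the general listing and can appear as the maximum for its group and timepoint. An unplanned reading enters the windowed summaries only when the planned visit has no data (SAP Appendix 1); otherwise it appears only in the general listing.

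**The case against.** A reader might infer that high readings would go unlisted, or that the report could declare that no blood pressure was of clinical concern. The documents do not support either inference. The values are in the general listings, and planned ones feed the per-timepoint maxima. Protocol 9.5 separately commits to describing blood pressure abnormalities of potential clinical concern and to summarising abnormal and clinically relevant changes. Protocol 8.4 makes a finding an adverse event if it needs intervention or if the investigator or sponsor regards it as one. Protocol 3.3 includes clinically significant vital-sign abnormalities in the escalation rules. None of this depends on Appendix 2, and the primary endpoints are adverse events and anti-drug antibodies.

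The size can be challenged too. Reaching 189/109 uncounted needs a baseline at both entry limits and rises that stop just short of both triggers. Protocol Table 1 gives no baseline blood pressure, so the number of subjects who could come near it is unknown. Rises of 30/20 or more are counted for everyone.

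Finally, 140 and 90 are tabulation limits for ambulatory readings. The SAP does not call them criteria of clinical concern, and entry allows a systolic pressure up to 160. Applying them to cuff readings as the required limit would flag values that the protocol accepts at baseline.

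All of this stands, and it limits the consequence to two outputs. It does not supply the missing category. A timepoint maximum does not say how many subjects were high or where they started, and the protocol's general commitments give no numerical reporting limit for a high cuff pressure.

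**Conclusion.** The point holds as a reporting gap. SAP 10.2.2.2 promises categories for maximum values that Appendix 2 does not contain for systolic or diastolic pressure. A high cuff reading reached by a rise below 30/20 mm Hg is left out of the categorical counts and of the listing of values of potential clinical concern, but not out of the report.

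The size is a matter of range: from 159/99 at a baseline of 130/80 to 189/109 at 160/90, assuming whole mm Hg and a baseline equal to the value shown. How many subjects are affected cannot be derived from the documents. The 40 planned SAD subjects are those with no ambulatory count at all, not a number expected to have unflagged high readings.

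The wrong appendix number and the standing-pulse row are editorial. The study is exploratory and descriptive, so no hypothesis test is affected. The correction is worth making because it is cheap and repairs a safety output that cannot be produced as described.

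**What to change.** 1. In SAP 10.2.2.2, cite Appendix 2. The same reference in SAP 10.2.2.3 needs the same correction.
2. In Appendix 2, add an absolute upper reporting category for supine systolic and supine diastolic pressure. The sponsor should set and state the limits; those already used for ambulatory readings (above 140 and above 90 mm Hg) are one documented option.
3. Tabulate the new category separately for subjects at or below the limit at baseline and for those above it.
4. In the listing of values of potential clinical concern, print the baseline value beside each reading so that unchanged pre-existing hypertension can be recognised.
5. Optionally, delete the standing-pulse row.

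The cost is two table rows, a corrected reference and one listing column, all from data already collected. The downside is that some subjects with known hypertension will be counted, which items 3 and 4 make visible. The table shells in Appendix 4 are still to be provided, so the change can be made before they are drawn up. It is a reporting category only and alters no clinical management rule.

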10.2.2.3. ECG Data

For each planned timepoint, baseline values and change from baseline values within each treatment will be summarized with descriptive statistics (using sponsor default standards). Absolute values and changes from baseline in PR, QT, QRS, heart rate, and QTcF will be summarized by treatment, and study day using the sponsor reporting standards. Mean plots (change from baseline values only), individual plots and tables for both observed values and change from baseline will be generated.

Changes from baseline in QTcF will be plotted separately against baseline for each planned study days per study window. These will be presented in scatter plots for all observations where QTcFs are recorded. Different symbols will be used for each treatment.

Maximum increase from baseline for QTcF, heart rate, QT, PR and QRS will be summarized by treatment and day. The number and percentages of subjects with QTcF interval ≥ 500 msec at any post-baseline time point will be summarized. The incidence of maximum post-dose QTcF values and maximum increases from baseline will be summarized descriptively (counts and percentages) according to the following categories:

Table 6. QTcF Category

QTcF (ms)	450 - < 480	480 - < 500	≥ 500
QTcF (ms) increase from baseline (ms)	30 - <60	≥ 60	

If more than one ECG is collected at a nominal time post dose, the mean of the multiple measurements will be used to represent a single observation at that time point for summary statistics tabulation. Changes from baseline will be defined as the change between QTcF post-dose and from the pre-dose values on Day 1. ECG endpoints and changes from baseline (QTcF, PR, QRS) will also be summarized descriptively by treatment using categories as defined in [Appendix 1](#) (for QTc these correspond to ICH E14). Numbers and percentages of subjects meeting the categorical criteria will be provided. All planned and unplanned postdose timepoints will be counted in these categorical summaries. All values meeting the criteria of potential clinical concern will be listed.

Listings of subjects with any single change from baseline in QTcF \geq 60 msec or postdose value \geq 500 msec will also be produced. These data will be listed in accordance with the sponsor reporting standards.

10.2.2.5. Ambulatory Blood Pressure Monitoring (ABPM)

For MAD portion of the study, ambulatroy blood pressure (ABP) reading will be acquired using the ABPM equipment provided by Biomedical Systems to evaluate potential treatment effect on ABP. Ambumlatory blood pressure are scheduled to be recorded at the following visits:

Table 7. ABPM Visit Schedule

Protocol Visit	Visit code to be selected
Day-2 / Day -1	Day -2
Day 1/ Day 2	Day 1
Day 7/ Day 8	Day 7
Day 63/ Day 64	Day 63
Day 84/ Day 85	Day 84
Unscheduled	UNS
Certification	CERT
Test	TEST

Summary of ABPM measures mSBP, mDBP, mHR, and mMAP represent weighted means of systolic blood pressure, diastolic blood pressure, heart rate and mean arterial pressure (MAP), respectively, and will be summarized in three time increments for a given measurement period: 24 Hour, Day Time (06:00 – 22:00), and Night Time (22:00 – 06:00). mXXX will be calculated using an area under the curve approach over the collection time interval, normalized by the time interval: $AUC(0-t) / t$. Mean over study days by treatment line plots will be produced along with spaghetti plots of individual profiles over study days grouped by treatment. The number and percentage of subjects with SBP > 140 mmHg, and DBP > 90 mmHg will be tabulated by treatment and Study Day, respectively. Additionally, mSBP, mDBP, mHR, and mMAP response will be modelled using a MMRM with corresponding baseline as covariate, and treatment and visit as fixed factors. Mean change from baseline over time with active treatment may be compared to the mean change from baseline over time with pooled placebo treated subjects using MMRM analysis with treatment, visit, and visit by treatment as fixed effects, subject as a random effect, and baseline value as covariate adopting unstructured covariance structure. For displaying purpose, Mean(\pm SE) of hourly average of absolute SBP, DBP, HR, MAP, and change from baseline will be plotted by Study Day and 24-hour time per treatment group; by treatment and 24-hour time per Study Day. Line plots of individual 20-min measurements of each subject will be plotted by study Day and time, and group by treatment and dose group. Least square means (\pm SE) of day Time, Night Time, and 24 Hour mSBP, mDBP, mHR, and mMAP will be plotted by treatment and Study Day. If warranted, a longitudinal Emax model may be developed to further characterize the potential treatment effect on ABPM.

10.2.2.6. Injection Site Reaction Evaluation

The injection sites were assessed for erythema, induration, ecchymosis, injection site pain, injection site pruritus, or other observed characteristics after investigational product administration. Injection site reaction evaluation will be summarized by dose and reaction response over time.

10.2.2.7. Other Safety Data – Screening and Other Special Purpose Data

The number and percentage of subject receiving study treatment administration will be summarized. The immunogenicity findings, for anti-drug PF-06293620) antibodies (ADA) will be summarized. All concomitant medication(s) as well as non-drug treatment(s) will be provided in the listings.

10.2.3. PK Analyses

10.2.3.1. Concentrations below the limit of quantification

In all data presentations (except listings), concentrations below the limit of quantification (BLQ) will be set to zero. (In listings BLQ values will be reported as “<LLQ”, where LLQ will be replaced with the value for the lower limit of quantification.)

10.2.3.2. Deviations, missing concentrations and anomalous values

In summary tables and plots of the median values at each time point, statistics will be calculated having set concentrations to missing if 1 of the following cases is true:

1. A concentration has been collected as ND (ie not done) or NS (ie no sample),
2. A deviation in sampling time is of sufficient concern or a concentration has been flagged anomalous by the pharmacokineticist.

Note that summary statistics will not be presented at a particular time point if more than 50% of the data are missing.

10.2.3.3. Pharmacokinetic parameters

Actual PK sampling times will be used in the derivation of PK parameters.

If a PK parameter cannot be derived from a subject's concentration data, the parameter will be coded as NC (ie not calculated). (Note that NC values will not be generated beyond the day that a subject discontinues.)

In summary tables, statistics will be calculated by setting NC values to missing; and statistics will not be presented for a particular treatment if more than 50% of the data are NC. For statistical analyses (ie analysis of variance), PK parameters coded as NC will also be set to missing.

If an individual subject has a known biased estimate of a PK parameter (due for example to an unexpected event such as coughing during or immediately after inhalation before all of the drug is absorbed by the body), this will be footnoted in summary tables and will not be included in the calculation of summary statistics.

To assess the pharmacokinetics of PF-06293620, PK parameters will be listed and summarized for subjects in the PK analysis set (as defined in [Section 7](#)). Missing values will be handled as detailed above.

The PK parameters to be summarized by treatment are outlined in Table 8.

Table 8. SAD and MAD Cohorts PK Parameters:

Parameter	Summary statistics
SAD Cohort	
AUC _{inf} , AUC _{last} , C _{max} , V _z /F, V _{ss} , CL/F, CL, AUC _{inf} (dn), AUC _{last} (dn), C _{max} (dn)	N, arithmetic mean, median, cv%, standard deviation, minimum, maximum, geometric mean, geometric CV%.
T _{max}	N, median, minimum, maximum.
t _{1/2}	N, arithmetic mean, median, cv%, standard deviation, minimum, maximum.
MAD Cohorts	
AUC _τ , C _{max} , C _{min} , CL/F, C _{av} , V _z /F, R _{ac} , R _{ac,Cmax} , AUC _τ (dn), C _{max} (dn), C _{min} (dn)	N, arithmetic mean, median, cv%, standard deviation, minimum, maximum, geometric mean, geometric CV%.
T _{max}	N, median, minimum, maximum.
t _{1/2}	N, arithmetic mean, median, cv%, standard deviation, minimum, maximum.

SAD Cohorts: To assess the relationship between the PK parameters and dose, dose normalized AUC_{inf}, AUC_{last} and C_{max} will be plotted against dose (using a logarithmic scale), and will include individual subject values and the geometric means for each dose. Geometric means will have a different symbol than the individual values. The values will be dose normalized (to a 1 mg/kg dose) by dividing the individual values and raw geometric means by dose. A footnote will be added to the plots to indicate that geometric means are presented on the plot.

Absolute/Relative bioavailability will be estimated as the ratio of dose-normalized adjusted geometric means for SC and IV for AUC_{last} and AUC_{inf}.

MAD Cohorts: To assess the relationship between the PK parameters and dose, dose normalized AUC_τ and C_{max} on Days 1 and 57, and dose normalized C_{min} on Day 57, will be plotted against dose (using a logarithmic scale), and will include individual subject values and the geometric means for each dose. Geometric means will have a different symbol than the individual values. The values will be dose normalized (to a 1 mg/kg dose) by dividing the individual values and raw geometric means by dose. A footnote will be added to the plots to indicate that geometric means are presented on the plot.

Dose-normalized natural log transformed AUC (SAD): AUC_{inf} (data permitting) and AUC_{last} ; and $AUC\tau$ (MAD) will be analyzed using a mixed effect model with treatment as fixed effects and subject as a random effect using a one-way analysis of variance (ANOVA). Estimates of the adjusted mean differences (Test-Reference) and corresponding 90% confidence intervals will be obtained from the model. The adjusted mean differences and 90% confidence intervals for the differences will be exponentiated to provide estimates of the ratio of adjusted geometric means (Test/Reference) and 90% confidence intervals for the ratios. SC is the Test treatment, and the IV is the Reference treatment.

Residuals from the model will be examined for normality and the presence of outliers via visual inspection of plots of residuals vs predicted values and normal probability plots of residuals but these will not be included in the clinical study report. If there are major deviations from normality or outliers then the effect of these on the conclusions will be investigated through alternative transformations and/or analyses excluding outliers. Justification for any alternative to the planned analysis will be given in the report of the study.

